Our long-term goal is to determine the pathophysiology of SD and related disorders, such as VT, and develop new diagnostic and treatment options for these patients. The objective of this application is to identify brain abnormalities in SD and SD/VT patients as the basis for characterization of central mechanisms underlying symptom improvement following the use of sodium oxybate. Our central hypothesis is that, compared to SD patients, SD/VT patients will have additional brain abnormalities within the sensorimotor brain circuits controlling voice production, which are being modulated to a greater extent with sodium oxybate treatment. We further postulate that the clinical efficacy of sodium oxybate treatment will correlate with its central modulatory effects. The rationale for the proposed research is that identification of distinct brain mechanisms underlying SD and SD/VT clinical manifestations would provide the necessary insights into the pathophysiology of these disorders, while understanding the neural correlates of sodium oxybate action would allow establishment of a scientific rationale for the use of a novel treatment in these disorders.

We propose the following two specific aims:

1. Determine disorder-specific brain abnormalities in SD and SD/VT patients. Based on our preliminary data, our *working hypothesis* is that distinct brain abnormalities will be present in SD and SD/VT patients, who also share common abnormalities within the sensorimotor brain networks controlling voice production.

2. Characterize the central effects of sodium oxybate treatment in ethanol-responsive SD and SD/VT patients. Based on our preliminary data, our *working hypothesis* is that the greater beneficial effects of sodium oxybate treatment in SD/VT patients compared to SD patients are due to a greater extent of modulation of their abnormal brain activation.

At the completion of these studies, it is our expectation that we will have (i) identified characteristic profiles of brain abnormalities in SD and SD/VT patients, (ii) determined the extent of their modulation with a novel treatment, sodium oxybate, both of which will be critical for (iii) establishment of neural markers and a new therapeutic option for patients who do not benefit from botulinum toxin treatment alone. These results are expected to have an important positive impact, because they will fundamentally advance our knowledge of the pathophysiology of SD and VT as well as allow for improved treatment.

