1.3.1 Study #1: Mapping disorder-specific brain activation in patients with SD vs. SD/VT using fMRI during symptomatic voice and speech production. We will use a sparse-sampling event-related BOLD fMRI design on a 3.0 Tesla Philips MRI scanner. We already successfully used this design for the investigations of voice and other laryngeal behaviors (Loucks et al., 2007; [name] et al., 2007; [name] et al., 2009; [name] and Ludlow, 2010). Brain activity will be studied during production of 10 symptomatic speech sentences (e.g., "We eat eels every day", "Sam has a rabbit in his hand") and syllables (repetitive vowel /i/ and continuous vowel /i/). In the scanner, subjects will listen to an auditory example of the task presented in a pseudorandomized order and reproduce it within the 5-s interval of the 'silent' period of scanning, only after which a 2-s image acquisition will follow, while the subjects remain silent and motionless. A resting condition without auditory presentation will serve as a baseline. Four scanning sessions will be acquired with a total of 36 experimental trials and 24 baseline conditions. Structural MRI will be acquired for an anatomical reference.

Data analysis will follow the similar processing pipeline as previously employed by us using AFNI software ([name] et al., 2007; [name] et al., 2009; [name] and Ludlow, 2010). Following initial data processing, the task-related responses will be analyzed using multiple linear regression with a single regressor for each task convolved with a canonical hemodynamic response function. Baseline drifts will be modeled using quadratic polynomials in time for each separate imaging run, and motion parameter estimates will be used as additional regressors of no interest in the multiple regression analysis. To account for disorder-specific vocal motor differences between SD and SD/VT groups, such as adductor and abductor voice breaks and shakiness, respectively, we will include the number of voice breaks and severity of voice tremor as variables in a within-group statistical analysis. Quantitative measures of SD and VT symptoms will be derived from the *Study 1.3.3* within this Aim. The correction of individual statistical parametric maps for multiple comparisons will be performed using Monte-Carlo simulations (Forman et al., 1995), which will identify a minimum cluster size at a voxelwise threshold of 0.005 at overall significance level of a corrected $p \leq 0.025$.

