To date, oral medications are known to provide little relief from SD and VT symptoms, and, thus, these patients are not systematically prescribed any medications (Adler, 2000). However, some patients report anecdotal benefits from taking lorazepam, clonazepam, diazepam, gabapentin, as well as some receive anti-depressants and anti-anxiety drugs to cope with their disorder-associated depression and anxiety. Recently, a series of clinical trials have reported significant beneficial effects of sodium oxybate on symptom improvement in treatment-refractory hyperkinetic movement disorders, including dystonia and ET ([name] et al., 2005a; [name] et al., 2005b; Arpesella et al., 2009). This medication seems to target more efficiently the tremor symptoms. Hence, it is possible that it may represent an alternative treatment option for SD/VT patients, whose symptoms are not fully responsive to botulinum toxin treatment.

However, despite remarkable improvement of symptoms in patients with movement disorders, the central effects of sodium oxybate also remain unknown. The absence of such information is a significant problem because it prevents the development of a scientific rationale for the use of a potentially beneficial novel pharmaceutical agent for the treatment of SD and VT. The objective of this aim is, therefore, to identify the mechanisms of central action of a promising novel medication, sodium oxybate, in SD and SD/VT patients as well as to determine the extent of central effects of a combined use of sodium oxybate and botulinum toxin treatments. Our working hypothesis is that the greater beneficial effects of sodium oxybate treatment in SD/VT patients compared to SD patients are due to a greater extent of modulation of their abnormal brain activation. This hypothesis has been formulated based on our preliminary data and will be tested using the experimental approach of fMRI during symptomatic speech production before and after treatment in SD and SD/VT patients, who report improvement of their symptoms after alcohol intake. The rationale for these studies is that the explanation of central mechanisms of action of sodium oxybate in SD and VT patients would help establish a scientific rationale for this drug as a new treatment option for patients who have failed other therapies.

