Sodium oxybate was administered in the office by mouth. Pre- and one hour post-drug voice and speech examinations were performed and videotaped. Initial dose was 1 gm three times daily. It was increased individually every two weeks, until a dose was achieved that improved symptoms without undesirable side effects. The target dose was 1.25 gm T.I.D., although the dose required to achieve benefits varied between patients and correlated with the dose of alcohol required to achieve a similar result. Sodium oxybate was well tolerated by all patients without tolerance and rebound. Based on blinded acoustical analysis of voice and speech samples, SD-related symptoms (breaks, harshness and breathiness) improved over 36% from baseline, whereas voice tremor improved over 71% from baseline. Some patients continued sodium oxybate treatment together

with botulinum toxin injections after study completion. These patients reported that such combined use helped prolong the botulinum toxin injection cycle in addition to relieving VT symptoms.

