2.3 Research Design

The following 2 groups of patients will participate in the proposed studies of Specific Aim #2: (1) SD patients, and (2) SD/VT patients. Because sodium oxybate has been shown to be effective in patients with movement disorders who self-report symptom improvement after alcohol intake, only ethanol-responsive patients will be recruited for the purposes of these studies. We estimate that 60% of ethanol-responsive patients per group, who participated in the studies in Specific Aim #1, will also participate in the studies in Specific Aim #2. Both ADSD and ABSD patients will be included and closely matched with ADSD/VT and ABSD/VT patients. Patients will be identified according to the screening and detailed examinations as described in Specific Aim #1. In this Specific Aim, we will (1) evaluate the central effects of sodium oxybate in SD and SD/VT patients to determine the relationship between improved clinical symptoms and modulated brain function, and (2) examine the extent of central effects from the combined use of sodium oxybate and botulinum toxin treatments as an alternative treatment schedule for patients with limited benefits.

2.3.1 Study #1: Mapping central effects of sodium oxybate treatment in patients with SD and SD/VT using fMRI during symptomatic speech production. Similar to the fMRI study under Specific Aim #1, we will use a sparse-

sampling event-related BOLD fMRI design during symptomatic voice and speech production on a 3.0 Tesla Philips MRI scanner. Each patient will participate in 2 fMRI sessions, before and after treatment with sodium oxybate. All recruited patients will have to be symptomatic; if they are treated with botulinum toxin injections, they may be included only if they are symptomatic at the end of their botulinum toxin treatment cycle. During each scanning session, the patient will be asked to perform short English sentences as well as repetitive and continuous vowel /i/, designed to elicit SD and VT symptoms. Four scanning sessions will be acquired with a total of 36 experimental trials and 24 baseline resting conditions. Structural MRI will be acquired for an anatomical reference.

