Following the initial (baseline) fMRI session, patients will receive an individualized tolerable and efficacious single dose of sodium oxybate, given orally in the office. Patients' symptoms will be evaluated and videotaped one hour after receiving this dose with the immediately followed-up second fMRI session, during which the patients will be asked to produce the same tasks performed during the pre-treatment fMRI study. Patients' post-treatment scans will be compared to their pre-treatment scans to identify differences in brain activation abnormalities due to the effects of sodium oxybate treatment. Voice and speech production during both scanning sessions will be digitally recorded for acoustical analysis and correlations with the central effects of the treatment.

Data analysis. Using AFNI software, fMRI data analysis will include initial pre-processing followed by analysis of the task-related responses using multiple linear regression with a single regressor for each task convolved with a canonical hemodynamic response function, as described above in *1.3.1 Study of Specific Aim #1*. For group analysis, a two-way ANOVA will be conducted with subject as a random factor and task as fixed factor (corrected $p \leq 0.025$). Conjunction analysis at a cluster significance threshold of $p < 0.005$ will determine common and distinct regions of activation within the patient group during task production in the pre- and post-treatment fMRI sessions. Finally, pre- and post-treatment neuroimaging findings will be correlated with the behavioral data derived from acoustical analysis of voice and speech recordings.

Additionally, to determine the extent of sodium oxybate effects on speech network dynamics, we will re-examine functional and effective network connectivity using the same PPI and DCM procedures as described in the *Study 1.3.1*.

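### Aim 2 attributes symptom benefit to brain modulation, but its before/after contrast is activation evoked by speech that the drug is itself expected to change

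*Combined protocol and SAP*

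**What the plan says.** **The claim.** The Specific Aims page and section 2.1 (Aim 2, Introduction) both carry the working hypothesis that "the greater beneficial effects of sodium oxybate treatment in SD/VT patients compared to SD patients are due to a greater extent of modulation" of abnormal activation. Section 2.4 (Expected Outcomes) goes further and expects the drug's brain mechanisms to have been determined.

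**The evidence.** Section 2.1 says the hypothesis will be tested with the "experimental approach of fMRI during symptomatic speech production before and after treatment in SD and SD/VT patients". Section 2.3.1 adds: "Each patient will participate in 2 fMRI sessions, before and after treatment with sodium oxybate". The tasks are sentences and vowels "designed to elicit SD and VT symptoms", and rest is the only other condition. Post-treatment scans are compared with pre-treatment scans "to identify differences in brain activation abnormalities due to the effects of sodium oxybate treatment".

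**The analysis.** The data analysis paragraph of 2.3.1 has one regressor per task, with a reference back to section 1.3.1. It then gives a group ANOVA with subject and task as factors, a conjunction of pre and post maps, and a correlation of imaging findings with acoustic measures. It also repeats the PPI and DCM connectivity analyses. Section 2.3.2 uses the same pipeline.

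**Voice performance.** For Aim 1, section 1.3.1 says: "we will include the number of voice breaks and severity of voice tremor as variables in a within-group statistical analysis", to account for vocal motor differences between the groups. The Aim 2 analysis does not name these variables. The material exists, however: "Voice and speech production during both scanning sessions will be digitally recorded".

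**The concern.** Voice breaks and tremor are motor events with auditory and sensory consequences. If the drug makes the voice smoother, the second scan records the response to a different vocal act. A fall in speech-evoked activation may then come from drug action in that region, from the changed output and feedback, or from both. The same applies to a larger fall in SD/VT than in SD, and to a correlation between the fall and the benefit.

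What is at stake is the conclusion of Aim 2. Without some account of vocal performance, regions that merely accompany a better voice could be reported as regions that the drug modulates, and the step from *accompanied by* to *due to* would have no support in the analysis.

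**Working it through.** The plan gives no figure that decides this point, so the check sets its sections side by side and then asks what the planned correlation can show.

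**1. Is the voice expected to differ between the two scans?** Yes. In the pilot (2.2.2, part I), "SD-related symptoms (breaks, harshness and breathiness) improved over 36% from baseline, whereas voice tremor improved over 71% from baseline". These figures are by symptom type, in a mixed pilot of 2 SD and 4 SD/VT patients. They show that vocal output changes under the drug. They are not an SD figure and an SD/VT figure.

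**2. Does the plan accept that vocal symptoms bear on activation?** Yes, for Aim 1: section 1.3.1 adds breaks and tremor severity for that reason. In Aim 2 the same quantities are expected to change within each patient between scans, so the reason applies at least as strongly.

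**3. Does any stated Aim 2 analysis separate drug action from vocal performance?**
- The ANOVA names subject and task, and no voice term.
- The conjunction compares maps, and both maps contain the response to speaking.
- As described in 1.3.1, PPI and DCM concern influences between brain regions, not between brain and voice.
- No symptom-free task, performance-matched trials or separate analysis of rest is described, and section 2.5 does not raise the matter.

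**4. What can the correlation show?** Let the first link in the chain be X, with mean m and between-patient SD s, and the second link Y = X + error, with error SD e. In one chain X is the brain change and Y the voice change; in the other the roles are swapped. Either way:
- the mean group difference in activation change is m₂ − m₁;
- the within-group brain-voice correlation is s / √(s² + e²).

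With assumed s = 0.35:

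| e (assumed) | Formula | Simulated r, both directions | Chance of significance in both groups (brain first v voice first) |
|---|---|---|---|
| 0.20 | 0.35/√0.1625 = 0.87 | 0.86 | 1.00 v 1.00 |
| 0.35 | 0.35/√0.2450 = 0.71 | 0.70 | 0.92 v 0.91 |
| 0.50 | 0.35/√0.3725 = 0.57 | 0.56 to 0.57 | 0.56 v 0.56 |

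The simulation used 22 patients per group (the calculated size in 2.3.1), 4,000 runs and a 0.025 level. The values of s and e are illustrative; only the equality of the two directions matters. The chains do differ in the spread of the activation change (s against √(s² + e²)), but neither value is known in advance, so this does not identify the direction.

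**5. Is there outside support in the plan?** Some, and it is mixed. Section 2.1 cites two studies after botulinum toxin injection into the laryngeal muscles. Both found lower activation in thalamus and basal ganglia, and the PET study also found it in motor cortex and cerebellum. Basal ganglia, thalamus and cerebellum are also among the regions lowered by sodium oxybate in the pilot (2.2.2, part II). But the fMRI study found no cortical change, and the PET study found increases in sensory association areas, operculum and midbrain. The plan itself calls these results conflicting and the mechanism unclear.

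**The case against.** The strongest reply has four parts.

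- **The drug acts centrally.** Section 2.2.1 describes a drug that crosses the blood-brain barrier and is converted to GABA in the brain; no laryngeal action is described. This stands. A reader might infer that the plan has cause and effect reversed, but the documents do not support that. What remains open is which regions are sites of action and how much of the change in each reflects altered voice.
- **The cross-reference may already bring in the voice variables.** Section 2.3.1 points to 1.3.1 for the regression. That is possible, so one cannot say that Aim 2 has no voice adjustment. The text is ambiguous: it lists task regressors and does not name the voice variables.
- **Activation need not follow symptoms.** The mixed botulinum findings bear this out, so a better voice *may* lower activation; it is not shown to. Images are also acquired in silence after the speaking window, so the signal is activation evoked by speaking, not recorded during it.
- **Adjustment does not settle direction.** Correct. If the drug changes the brain and the brain changes the voice, symptom severity lies on the causal path, and adjustment removes that part of the effect. Accepting a region as a site of action only if its change survives adjustment would reject true sites.

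It is also fair to note that *due to* is labelled a working hypothesis, and that the Specific Aims page separately predicts only that efficacy will correlate with central effects.

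**Conclusion.** The point stands as a limit on interpretation. The planned contrast can show that speech-evoked activation changes after the drug, and that the change goes with symptom benefit. It cannot show that benefit is caused by modulation in the regions found, because altered vocal output may contribute and no stated analysis addresses that. This rests on two things: that the drug changes the voice, which the pilot supports, and that vocal symptoms can influence activation, which section 1.3.1 accepts.

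No numerical size is given. A reader might take 36% and 71% as the SD and SD/VT effects, apply them to the activation excess in the Aim 1 sample-size paragraph, and obtain a rate of spurious findings. The documents do not support that step. The percentages are by symptom type in a mixed pilot, the share of the excess that tracks symptoms is unknown, and the planned test is voxelwise and corrected rather than a single-region test at 0.025. Nor would the result be a type I error rate, since in that scenario activation really does change.

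The change is worth making because it is cheap and alters what Aim 2 can conclude.

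**What to change.** In 2.3.1, and in 2.3.2 which inherits its analysis:

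1. State whether the voice variables of 1.3.1 apply to Aim 2.
2. Report the pre/post contrast twice: unadjusted, and with symptom severity (breaks, tremor) scored from the scanner recordings as a covariate. Centre the covariate on one common pre-plus-post value per patient. Centring each session on its own mean would leave the between-scan voice difference in the contrast.
3. Fix the reading in advance. A change that persists after adjustment is evidence against a pure performance explanation. A change that disappears is undetermined (performance effect or mediation) and does not show that the region is not a site of action.
4. Replace *due to* in the Specific Aims and section 2.1 with *accompanied by* or *associated with*, and bring section 2.4 into line.
5. State in 2.3.2 that the third scan is recorded as well; 2.3.1 mentions only its own two sessions.

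**Cost.** Scoring is modest work on recordings already planned. Patients whose Aim 1 scan serves as their baseline are covered, since 1.3.4 plans recording during scanning. The adjusted estimate will be imprecise: there are 36 trials per scan, spread over sentences and two vowel tasks. If few trials overlap in severity between scans, the comparison at a common value becomes extrapolation. It also removes any effect truly mediated through the brain, which is why both estimates are needed.

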1.2 Justification and Feasibility

1.2.1 Review of Relevant Literature. Considerable progress has been made recently in the identification of brain functional and structural alterations in SD patients using neuroimaging techniques, such as fMRI, positron emission tomography (PET), DTI and high-resolution MRI (Haslinger et al., 2005; Ali et al., 2006; [name] et al., 2008; [name] and Ludlow, 2010, 2011). These studies have consistently found functional abnormalities in the laryngeal sensorimotor cortex, basal ganglia, thalamus, and cerebellum as well as structural white matter alterations within the corticobulbar, basal-ganglia-thalamo-cortical and cerebello-thalamo-cortical circuits. Further, using a combination of high-resolution MRI and fMRI in SD patients, a significant relationship has been identified between gray matter structural and functional alterations in the key structures of the speech control system, including the laryngeal sensorimotor cortex, inferior frontal (IFG), superior temporal and supramarginal gyri, and cerebellum ([name] and Ludlow, 2011). The severity of SD voice breaks has been reported to positively correlate with white matter alterations in the ventral thalamus ([name] et al., 2008) and with gray matter changes in the IFG and cerebellum ([name] and Ludlow, 2011). Substantiating these findings, postmortem tissue examination found focal axonal degeneration and demyelination in the genu of the internal capsule and mineral accumulations in the basal ganglia, thalamus, and cerebellum in one ADSD patient ([name] et al., 2008) as well as clusters of microglial activation in the brainstem nuclei associated with laryngeal control in two ADSD patients ([name] et al., 2010). The results of these studies indicate that functional and structural abnormalities do exist in SD patients and that they are coupled with functional abnormalities at different levels within the speech production system, possibly contributing to SD symptom elicitation. However, these studies do not report any direct comparisons between SD and SD/VT patients, hence, they contribute little to complete understanding of VT, which is a prominent feature in about 1/3 of SD patients.

Although the central mechanisms of VT either in isolation or in combination with SD are unknown, studies in other forms of essential tremor (ET) have revealed several brain abnormalities, which may also be present in VT. Specifically, studies in animal models of action-induced tremor have shown abnormal functioning of the central oscillator in the Guillain-Mollaret triangle located in the brainstem and involving the inferior olivary nucleus (Elble, 1998). In a series of neuropathological studies in ET, degenerative changes have been found with predominant cerebellar pathology, such as Purkinje cell loss and an abundance of Purkinje cell axonal torpedoes without Lewy bodies inclusions (Louis et al., 2006; Louis et al., 2007; Axelrad et al., 2008; Louis and Vonsattel, 2008; Louis et al., 2009). Neuroimaging studies have further disclosed abnormal function and structure in the prefrontal cortex, parietal lobule, thalamus and cerebellum (Boecker et al., 1996; Berg et al., 2000; Nitschke et al., 2001; Benito-Leon et al., 2009). Some have also pointed to deficient GABAergic transmission as a contributing factor in the development of ET (Sinton et al., 1989; Boecker et al., 1996; Mally et al., 1996).

Collectively, these studies demonstrate the presence of alterations in functional and structural brain organization in SD and possibly VT patients. Further research is needed to better understand the co-occurrence of these disorders and their pathophysiological mechanisms in order to develop more efficient pharmacological treatments.

